4.0 STUDY DESIGN & METHODS

1. Design

This prospective longitudinal cohort study will evaluate the effectiveness of a quadrivalent HPV VLP vaccine in an HIV-positive cohort of girls and women in multiple centres across Canada.

2. Rationale

This study presents a unique opportunity to understand the long term impact of HPV vaccination in immune compromised women. Our prior study demonstrated that although women and girls living with HIV in Canada have complicated lives and have a high burden of socioeconomic disadvantages, they are very interested and committed to participating in research. This is clearly demonstrated by the degree of engagement of positive women in the National Consensus Statement on Women, Trans People and Girls and HIV Research in Canada. Our study sites across the country have been highly effective at engaging with this challenging population

through their long-standing, dedicated clinics. We have a cohort of over 400 girls and women who continue to live with their HIV disease and will require ongoing specialized HIV care for the rest of their lives. As they are just completing the first protocol out to 24 months and are for the most part still attending for care, with 94% remaining engaged with our study groups. We are confident that we can effectively re-engage them in our follow-up study. It is vital that this study be launched now while most participants are at 24-36 months from vaccine course, and key follow up timed sampling can ascertain the trajectory of antibody responses as well as the course of HPV disease.

Parallel studies in HIV-negative women, some being conducted by members of our investigator group, in Canadian cohorts, are ideal for comparison purposes. For example, there are over 1,000 girls enrolled in Quest, the long term follow up of the 2 dose/3 dose study of the qHPV vaccine in healthy volunteers in Canada ([name]/[name]). This permits patient level data to be compared directly with inclusion of known confounders in the analysis. We have support from Merck (see appended letter of support) for the competitive Luminex immunoassay (cLIA) assay to ensure consistency and comparability to both our prior study antibody titres and to the published literature on qHPV antibody responses. To date, all qHPV vaccine studies in the published literature, including those conducted by our investigator group, have had the antibody assays conducted through Merck laboratories. This provides an extraordinary ability to conduct robust comparisons of immune responses across study populations who have been given the qHPV vaccine.

5.0 STUDY COHORT

1. Population

Four hundred and seven (407) HIV-positive girls and women (greater than, or equal to, age 11) attending the HIV treatment clinics in each of the 13 sites across Canada and who have enrolled in the original study “A Study of an HPV VLP Vaccine in a Cohort of HIV Positive Girls and Women (CTN 236)” will be offered participation in the study.

Inclusion Criteria

- Enrolled in CTN 236 study
- Able to give fully informed consent or assent

Exclusion Criteria

- Did not receive at least one vaccination via CTN 236, phase 1
- Cannot provide fully informed consent or assent

2. Delays and contraindications to subsequent study procedures

5.2.1 Indications for a delay in genital sampling

- Pre-menarchal and not sexually active – no genital sampling until post-menarchal and sexually active or at the discretion of the investigator
- Subjects must not be menstruating at the time of a genital sampling. A study visit may need to be delayed until menses has stopped or the subject may have all other study procedures performed and the subject will have to be brought back to the clinic for genital sampling.

6.0 STUDY CONDUCT

1. Adherence to Industry Guideline and Regulations

This trial is to be conducted in accordance with the protocol and ICH GCP.

All study staff should be familiar with the following document:

ICH GCP: <http://www.ich.org/cache/compo/276-254-1.html>

All investigators and their investigative sites are obligated to comply with investigator responsibilities, monitoring, and archiving data, audits, confidentiality, and publication requirements.

The Study Coordinating Centre shall also accept the responsibilities of the Sponsor as outlined in ICH GCP.

2. Ethical conduct / research ethics board (REB)

Each site will be required to utilize a REB that conforms to section 3 of the GCPs: 3.1 Responsibilities, 3.2 Composition, Functions and Operations, 3.3 Procedures, 3.4 Records.

Prior to the conduct of this trial, the protocol, consent form, and all related documents must be submitted to the REB at each site. Approval for this study must be granted before the trial can be started at that site.

The Principal Investigator at each site will forward a copy of the REB approval to the Study Coordinating Centre before the first subject is enrolled in the study at that site. All amendments to the protocol that affect the safety and/or welfare of the study participants shall be submitted to the site REB and approved prior to implementation.

All study staff should be familiar with the Tri-Council Policy Statement on Ethical Conduct for Research Involving Humans:

<http://www.pre.ethics.gc.ca/english/policystatement/policystatement.cfm>

3. **Informed Consent/ Assent**

Typically, each subject and parent/legally authorized representative (if applicable) must participate in the informed consent process and sign and date the informed consent form before any procedures specific to this protocol are performed on that subject.

A modified recruitment method may be utilized if clinical care flow for a patient would be excessively interrupted by research. To ensure clinical history and pelvic examination occur in a timely manner, a HPV in HIV researcher may not always have the opportunity to speak with a potential study participant prior to a pelvic examination. In these circumstances prior to the routine pelvic exam, the attending clinician will request verbal permission to collect two additional vaginal swab samples and a cytology sample during the exam for the purposes of this study. Ability to verbally consent, in these instances, will better respect both clinician and patient time and reduce participation burden by allowing for study sample collection to align with clinical sample collection.

After the exam, the HPV in HIV researcher will immediately follow up and meet with the patient to go over the full consent form, and answer any questions or concerns prior to their signing the informed consent document. If written informed consent is not provided, samples will be discarded.

Consenting *a posteriori* will confer benefits to the participating women as their clinical care flow will not be interrupted by research. Also, by obtaining verbal consent at the initial pelvic exam to obtain samples, we will minimize the discomfort, stress and inconvenience experienced by women that could otherwise be subjected to a second pelvic exam.

In the absence of a site SOP for informed consent, the site will write a note to file explaining the procedures followed while obtaining informed consent/assent.

At each subsequent study visit, subjects and parent/legally authorized representative (if applicable) will be asked if they wish to continue in the study and give their ongoing consent/assent to participate. This will be documented in the source documentation.

In accordance with the ICH Harmonized Tripartite Guidelines for GCP for those subjects who can be enrolled in the trial with the consent of the subject's legally acceptable representative (e.g. minors), the subject should be informed about the trial to the extent compatible with the subject's understanding and, if capable, the subject should sign and personally date a written informed assent. It is required that the assent be signed by each subject, if capable, in addition to the informed consent that is to be signed by her legal representative.

A young subject who originally signed an assent form who becomes menarchal and sexually active will be required to sign a consent form that includes the study genital sampling prior to performing any of these procedures.

Study consent forms and assent forms and above outlined use of verbal consent must be approved by a REB at the particular study site.

An informed consent form template and assent form template are included in the protocol appendices and may be amended as per site and REB requirements. REB approved consent and assent forms for each site are to be sent to the Study Coordinating Centre and updated as necessary.

4. Source Documentation

Study source documentation should be kept for each subject at the study site. Source data is raw data such as original laboratory records, documentation, documentation of original observations and activities. Source data is the first time and place an observation is documented, for example the documentation of a blood pressure.

Study source documentation should be captured separately in the subject study chart; however, when the original source data is such that it cannot be placed with the subject source document chart, for example, the source data is contained in the hospital patient chart, sites may take a photocopy of the document and indicate on the photocopy where the data was first documented.

When source data is in electronic form, for example, laboratory results, a printout of the electronic data is to be printed and placed in the subjects source document chart.

A source document template will be provided to sites by the study coordinating centre. However, sites are not required to use the template if other approved methods of capturing source data are preferred. Alternate methods of capturing source data must be approved by the Study Coordinating Centre.

5. Monitoring

A representative of the Study Coordinating Centre will visit investigative sites during the first months of enrollment to ensure that all procedures are consistent with the protocol and that appropriate Standard Operating Procedures (SOPs) and essential study documentation are on file.

The sites will be monitored to ensure that the trial is being conducted in accordance with the protocol and ICH GCP.

Consent documentation will be reviewed at 100%. Source documentation/CRF reconciliation will occur at 20% at each site. Monitoring at each site will be based on enrollment at that site. A close-out of the study will occur after the Last Patient Last Visit has been conducted at each site.

Enrollment and study progress reports will be requested of the study sites at a frequency to be determined by enrollment rates.

7.0 STUDY PROTOCOL

1. Participant identification number (PID#) assignment

For this long term follow-up study of CTN 236, subjects will not be assigned new study numbers and will remain with the study number assigned as part of CTN 236.

7.2.1 Females aged 11-18 who are pre-menarchal and not sexually active

Adolescents and young women will be offered enrollment in the setting of established and experienced pediatric clinics. There are young girls with HIV infection, primarily perinatally acquired, who may be unaware of their diagnosis and the actual terminology of HIV. This is standard practice for care of children up to age 12 with a complex diagnosis with profound social stigmatization issues.

Those that are aware of the HIV terminology will receive the information and consents with HIV specific information. The term "immunocompromised" has been used in place of HIV in documents and

Research Protocol
Long Term Follow-up Study of CTN 236 - A Study of an HPV VLP Vaccine in a
Cohort of HIV Positive Girls and Women

templates that may be viewed by these young women (e.g. consent forms). Each site may use the standard terminology used at their site.

Those girls and women who are pre-menarchal and not sexually active will not have the same degree of disease endpoint evaluations (i.e. will not have any pelvic examinations or Pap smears until post menarchal and sexually active or at the discretion of the site investigator).

A young subject who originally signed an assent form who becomes menarchal and sexually active will be required to sign a consent form that includes the study genital sampling prior to performing any of these procedures.

7.2.2 **Changes to study procedures in pregnancy**

In the event of pregnancy Pap testing and genital study sampling will continue; however, an Ayre spatula will be used to collect cervical samples in place of the cytobroom until 3 months post-pregnancy.

3. **Summary table of study visits**

| | Visit Window | Ongoing Consent/Assent | Incl/Excl or Contraindication Criteria | Clinical Laboratory Investigations | Study Blood-Work (serology) | Pelvic Exam& Vaginal Sample Collection * | Study Cervical Cytology and HPV DNA * | SAE/Med Hx and Con Med/Exposure Update |
|---------------------|---------------------------------------|------------------------|--|------------------------------------|-----------------------------|--|---------------------------------------|--|
| Month 36 (Visit 8) | First Dose + 36 months (+/- 2 months) | X | X | X | X | X | X | X |
| Month 48 (Visit 9) | First Dose + 48 months (+/- 2 months) | X | X | X | X | X | X | X |
| Month 60 (Visit 10) | First Dose + 60 months (+/- 2 months) | X | X | X | X | X | X | X |
| Month 72 (Visit 11) | First Dose + 72 months (+/- 2 months) | X | X | X | X | X | X | X |
| Month 84 (Visit 12) | First Dose + 84 months (+/- 2 months) | X | X | X | X | X | X | X |

Research Protocol
Long Term Follow-up Study of CTN 236 - A Study of an HPV VLP Vaccine in a
Cohort of HIV Positive Girls and Women

| | | | | | | | | |
|------------------------|---|---|---|---|---|---|---|---|
| Month 96 (Visit 13) | First Dose + 96 months (+/- 2 months) | X | X | X | X | X | X | X |
|------------------------|---|---|---|---|---|---|---|---|

* Those girls and women who are pre-menarchal and not sexually active will not have any pelvic examinations or Pap smears until post-menarchal and sexually active or at discretion of the site investigator.

Due to variation in duration of time since first dose of vaccine, some subjects are out of window for Month 36 and Month 48, e.g. it has been more than 48 months since first dose of vaccine was received. Therefore, we have extended the study visit timeline up to and including Month 96 post-vaccine, also designated Visit 13. Visits will occur annually until project grant is completed (March 31, 2019).

4. Study Visits

7.4.1 Ordering of Study Procedures

At all visits - Study blood for serum antibody and cervical cytology/HPV DNA test and vaginal samples are to be done within a 24 hour period. Any deviations to the above exceptions must be documented in the source document and reported to the Study Coordinating Centre.

One time point - Lower Urinary Tract Symptoms Survey

This survey is a one-time cross sectional measure of lower urinary tract symptoms in participants above age 18. Questionnaires will be completed varying months post-vaccination, in line with varying enrollment dates in the precursor study.

7.4.2 Study Visit Window

| Interval | Length of interval (months) | Recommended interval between scheduled visits (months) |
|---------------------------------|--------------------------------|--|
| First dose to Month 36/Visit 8 | (36 ± 2) | 12 |
| First dose to Month 48/Visit 9 | (48 ± 2) | 12 |
| First dose to Month 60/Visit 10 | (60 ± 2) | 12 |
| First dose to Month 72/Visit 11 | (72 ± 2) | 12 |
| First dose to Month 84/Visit 12 | (84 ± 2) | 12 |
| First dose to Month 96/Visit 13 | (96 ± 2) | 12 |

7.4.3 Outline of study visits

MOTNH 36/VISIT 8 (36 months from first vaccine):

- Assess ongoing consent/assent
- Health history update, Pap testing/treatment outside study, and any new/resolved health issues
- Update concomitant medication and exposure usage

- Review study blood work/genital sampling delay and contraindication criteria
- Height and weight
- Clinical laboratory investigations including resistance testing
- Study serology
- Assess menarchal and sexually active status

Post menarchal and sexually active girls and women and/or at the discretion of the site investigator ONLY:

- Pelvic examination, including
 - external genital examination (including genital warts assessment)
 - inspection of vagina and cervix
 - additional assessments as per local practice and/or clinically indicated (e.g. sexually transmitted infection screening samples, bacterial vaginosis, clinical Pap smear, etc.)
- Liquid based study cervical cytology and HPV DNA sample
- Vaginal microbiota swabs

MONTH 48/VISIT 9 (48 months from first vaccine):

- Assess ongoing consent/assent
- Health history update, Pap testing/treatment outside study, and any new/resolved health issues
- Update concomitant medication and exposure usage
- Review study blood work/genital sampling delay and contraindication criteria
- Height and weight
- Clinical laboratory investigations including resistance testing
- Study serology
- Assess menarchal and sexually active status

Post menarchal and sexually active girls and women and/or at the discretion of the site investigator ONLY:

- Pelvic examination, including
 - external genital examination (including genital warts assessment)
 - inspection of vagina and cervix
 - additional assessments as per local practice and/or clinically indicated (e.g. sexually transmitted infection screening samples, bacterial vaginosis, clinical Pap smear, etc.)
- Liquid based study cervical cytology and HPV DNA sample
- Vaginal microbiota swabs

MONTH 60/VISIT 10 (60 months from first vaccine):

- Assess ongoing consent/assent
- Health history update, Pap testing/treatment outside study, and any new/resolved health issues
- Update concomitant medication and exposure usage
- Review study blood work/genital sampling delay and contraindication criteria

- Height and weight
- Clinical laboratory investigations including resistance testing
- Study serology
- Assess menarchal and sexually active status

Post menarchal and sexually active girls and women and/or at the discretion of the site investigator ONLY:

- Pelvic examination, including
 - external genital examination (including genital warts assessment)
 - inspection of vagina and cervix
 - additional assessments as per local practice and/or clinically indicated (e.g. sexually transmitted infection screening samples, bacterial vaginosis, clinical Pap smear, etc.)
- Liquid based study cervical cytology and HPV DNA sample
- Vaginal microbiota swabs

MONTH 72/VISIT 11 (72 months from first vaccine):

- Assess ongoing consent/assent
- Health history update, Pap testing/treatment outside study, and any new/resolved health issues
- Update concomitant medication and exposure usage
- Review study blood work/genital sampling delay and contraindication criteria
- Height and weight
- Clinical laboratory investigations including resistance testing
- Study serology
- Assess menarchal and sexually active status

Post menarchal and sexually active girls and women and/or at the discretion of the site investigator ONLY:

- Pelvic examination, including
 - external genital examination (including genital warts assessment)
 - inspection of vagina and cervix
 - additional assessments as per local practice and/or clinically indicated (e.g. sexually transmitted infection screening samples, bacterial vaginosis, clinical Pap smear, etc.)
- Liquid based study cervical cytology and HPV DNA sample
- Vaginal microbiota swabs

MONTH 84/VISIT 12 (84 months from first vaccine):

- Assess ongoing consent/assent
- Health history update, Pap testing/treatment outside study, and any new/resolved health issues
- Update concomitant medication and exposure usage
- Review study blood work/genital sampling delay and contraindication criteria
- Height and weight

- Clinical laboratory investigations including resistance testing
- Study serology
- Assess menarchal and sexually active status

Post menarchal and sexually active girls and women and/or at the discretion of the site investigator ONLY:

- Pelvic examination, including
 - external genital examination (including genital warts assessment)
 - inspection of vagina and cervix
 - additional assessments as per local practice and/or clinically indicated (e.g. sexually transmitted infection screening samples, bacterial vaginosis, clinical Pap smear, etc.)
- Liquid based study cervical cytology and HPV DNA sample
- Vaginal microbiota swabs

MONTH 96/VISIT 13 (96 months from first vaccine):

- Assess ongoing consent/assent
- Health history update, Pap testing/treatment outside study, and any new/resolved health issues
- Update concomitant medication and exposure usage
- Review study blood work/genital sampling delay and contraindication criteria
- Height and weight
- Clinical laboratory investigations including resistance testing
- Study serology
- Assess menarchal and sexually active status

Post menarchal and sexually active girls and women and/or at the discretion of the site investigator ONLY:

- Pelvic examination, including
 - external genital examination (including genital warts assessment)
 - inspection of vagina and cervix
 - additional assessments as per local practice and/or clinically indicated (e.g. sexually transmitted infection screening samples, bacterial vaginosis, clinical Pap smear, etc.)
- Liquid based study cervical cytology and HPV DNA sample
- Vaginal microbiota swabs

5. Study Procedures in Detail

7.5.1 Informed Consent/Assent

Please refer to section 6.3 for detailed information on Informed Consent/Assent.

7.5.2 Medical History

General Medical Systems History

A review of health history including current medications will be conducted.

7.5.3 **Height and Weight**

Height and weight will be documented.

7.5.4 **Clinical Laboratory Investigations**

Clinical blood samples will be collected, handled, processed, and analyzed at site local laboratories as per local practices. At each visit in which clinical laboratory investigations are to be performed, results for the following laboratory tests will be collected as part of the study: Hgb, WBC, platelets, ALT, AST, ALP, bilirubin, BUN, serum creatinine, CD4, CB8 and HIV RNA quantitative PCR (viral load). Results of any Hepatitis B or C and resistance testing, including clade, will be updated whenever additional resistance testing is performed.

Clinical labs for study purposes may be collected within 3 months (+ or - 12 weeks) of the study visit date.

7.5.5 **Study Blood Work**

Ensure all blood tubes and cryovials are clearly labeled with the 5 digit PID#, collection date, and visit month. Study blood work must be collected within 24 hours of the study cervical cytology/HPV DNA sample.

7.5.6 **Pelvic Examinations**

Pelvic examinations will include:

- Inspection of external genital exam including a standardized assessment of genital warts using a tool provided by the Study Coordinating Centre,
- Speculum exam including clinical Pap smear (if clinically indicated),
- Clinical standard Pap tests will be collected, handled, and processed as per local practices. The clinical standard Pap test sample is to be collected PRIOR to study cervical cytology collection,
- If clinical Pap is not done at study visit, obtain the result of most recent clinical Pap performed,
- If clinically indicated, samples are to be collected for sexually transmitted infection screening samples, bacterial vaginosis, etc.
- Vaginal microbiota swabs

7.5.7 **Study Genital Samples**

Ensure samples are clearly labeled with the 5 digit PID#, collection date, and visit month. Cervical cytology/HPV DNA samples must be collected within 24 hours of the study blood work sample.

7.5.7.1 **Cervical Cytology and HPV DNA**

Cervical cells will be obtained using a broom shaped endocervical cytobrush. Insert brush into the endocervical canal until the smaller bristles meet the ectocervix. Press gently and rotate clockwise 5 times

to ensure adequate cell sampling. The brush is then immediately rinsed in the PreservCyt solution by pushing the brush into the bottom of the vial 10 times to force the bristles apart. To ensure all cells are released, swirl the brush vigorously. Securely seal the vial and discard the collection device.

Samples may be kept at ambient to 4 degrees Celsius at the local sites until recalled monthly by the Study Coordinating Centre. The samples will then be shipped to the Coordinating Laboratory for Cytology/HPV DNA (BCCDC) where the samples will be processed and forwarded to the appropriate lab for cervical cytology (Cervical Cancer Screening Laboratory of BC) and for HPV DNA testing ([name] lab).

HPV DNA types and cervical cytology results may not be available to sites until the end of the study. Clinical Paps are being done as per standard of care and follow up to abnormal cytology will be at the discretion of the Site Investigator in cases where the liquid based cytology samples are available.

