8.0 MANAGEMENT OF CERVICAL CYTOLOGIC ABNORMALITIES

All participants (except those pre-menarchal and not yet sexually active) will undergo clinical standardized Pap smear testing as per local site standards. Cytologic abnormalities will be managed according to local algorithms. Management of cervical cytologic abnormalities will be decided by the Site Investigator and may be based on the clinical standardized Pap smear or study cervical cytologies when available. It is suggested to manage abnormal results based on the higher grade of dysplasia.

Participants who have high grade or persistent low grade changes will be referred for follow-up evaluation by colposcopists involved with local HIV treatment centres. After obtaining consent to release medical records, all colposcopic, colpophotographic and histopathologic (biopsy) results will be added to the study record; slides from biopsies will be requested by the BC Cancer Agency for central confirmation of histopathologic diagnoses. Invasive cancers diagnosed during the study will be carefully documented and recorded once local, appropriate clinical management is provided. As in previous multicentre studies of high risk HIV positive women, we acknowledge variation in local colposcopic and treatment algorithms and anticipate imperfect compliance with referral for colposcopy; similarly, cervical disease endpoints (squamous intraepithelial neoplasia or dysplasia) in this study are cytologically and/or histologically defined as appropriate. Histopathology will be reported as cervical intraepithelial neoplasia grades, 1, 2 or 3 (CIN 1, 2 or 3), or carcinoma in situ.

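### Study cervical cytology may stay unavailable to sites until the study ends, with no release time or high-grade alert, so the referral rule may not reach an abnormality seen only on study cytology

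*Combined protocol and SAP*

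**What the plan says.** Three parts of the combined protocol and SAP bear on this.

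- **Release of results (7.5.7.1).** "HPV DNA types and cervical cytology results may not be available to sites until the end of the study". The next sentence gives the reason care is not meant to depend on them: "Clinical Paps are being done as per standard of care and follow up to abnormal cytology will be at the discretion of the Site Investigator", and it limits this to cases where the liquid-based samples are available. The only timing given concerns vials, which stay at the site "until recalled monthly by the Study Coordinating Centre".
- **Management (8.0).** Eligible participants "will undergo clinical standardized Pap smear testing as per local site standards". Decisions rest with the site investigator and "may be based on the clinical standardized Pap smear or study cervical cytologies when available". Then: "It is suggested to manage abnormal results based on the higher grade of dysplasia". The referral sentence is firmer: "Participants who have high grade or persistent low grade changes will be referred for follow-up evaluation by colposcopists".
- **The clinical Pap at the visit (7.5.6).** The visit includes "Speculum exam including clinical Pap smear (if clinically indicated"). When no Pap is taken, the site obtains the latest clinical result, with no limit on its age. When one is taken, it precedes the study sample.

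Section 13.0, item 2, has the study slides read at the provincial screening laboratory under its ordinary reporting rules, using Bethesda categories. It names no recipient and no turnaround.

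**The concern.** Section 8.0 accepts study cytology as a basis for management and says that high-grade changes will be referred. Section 7.5.7.1 allows that same cytology to be out of the site's reach for the whole study. A participant could meet the referral criterion on a slide already read by a screening laboratory while her site does not know it.

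This is a participant-safety point. The Background (1.0, item 3) says that HIV-positive women move faster from low-grade to high-grade lesions and to invasive cancer. The same section (item 10) reports LSIL or greater in 17% of this cohort at screening. That is not a high-grade rate, but it shows that abnormal cytology is not rare here.

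**Working it through.** **Step 1. Is there a release time or alert anywhere?** The plan states no figure to reproduce, so this is a reading of the text.

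| Section | Content | Release time or high-grade alert? |
|---|---|---|
| 7.5.7.1 | Results may be late; monthly recall of vials | No |
| 8.0 | Referral; study cytology used when the site has it | No |
| 9.0 | Reporting of SAEs that result in death | No |
| 13.0, item 2 | Ordinary laboratory reporting rules | None stated; silent on timing and recipient |
| 14.0 | Shipment of samples | No |
| 15.0 | DSMB meets twice a year | No cytology task given |

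**Step 2. When would study cytology be the only current cytology?** At a visit where a clinical Pap is not indicated, 7.5.6 lets an earlier result stand in. An abnormality that has appeared since then could show on the study slide alone. It could also do so where a concurrent clinical Pap misses the lesion.

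**Step 3. How long could a result wait?** Inputs: first visit of the first subject 10 June 2015 and last visit of the last subject 30 March 2019 (Summary, Timeline); visit windows of ±2 months (7.3, 7.4.2); completion defined as three annual visits (11.0). Assumption: results are held to 30 March 2019. One month is taken as 30.4375 days.

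- Longest wait, a sample taken on 10 June 2015: 1,389 days / 30.4375 = 45.6 months.
- A sample taken on 10 June 2018: 293 days / 30.4375 = 9.6 months, falling towards zero for the final visits.
- A completer sampled at all three visits, for example months 36, 48 and 60:
  - first to third sample, nominal 60 − 36 = 24 months; minimum (60 − 2) − (36 + 2) = 20 months;
  - second to third sample, nominal 60 − 48 = 12 months; minimum (60 − 2) − (48 + 2) = 8 months.

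The same spacing applies to 48 to 72, 60 to 84 and 72 to 96. Her third visit cannot fall after the last visit of the last subject. Under the assumption, 20 and 8 months are therefore lower bounds on the wait for her first and second results.

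Part of any wait is unavoidable. Monthly recall alone can take up to about one month, and the shipping and reading times that follow are not fully stated.

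**Step 4. How many participants?** This cannot be derived. The documents give neither the frequency of high-grade study cytology nor the share of visits without a clinical Pap.

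**The case against.** The strongest reply is that this is an open choice with its safeguard beside it. Clinical Paps under local standards apply to all eligible participants, and the condition in 7.5.6 governs only whether one is taken at that visit. Section 7.4.3 adds, at each visit, an update on outside Pap testing and treatment and, for eligible participants, inspection of the vagina and cervix. Study cytology comes on top of that care. This stands, and it is why the gap is limited to abnormalities seen only on the study slide. It does not close the gap, because an older clinical Pap cannot show a newer change.

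A second reply is that the answer may lie elsewhere. The Research Laboratory Manual (12.0) and the consent and assent templates (6.3) were not available for review, and the ordinary reporting rules in 13.0 might include prompt return. That is possible. But 13.0 is silent on timing, and 7.5.7.1 expressly allows late availability.

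A reader might also infer more than the text supports:

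- *That 7.5.7.1 and 8.0 contradict each other.* They do not. Section 8.0 uses study cytology only when the site has it.
- *That the higher-grade text is a rule being broken.* It is a suggestion. Only the referral sentence is firm.
- *That results must be withheld.* The wording permits lateness and does not direct it. Both sections expect some results to arrive in time to be used.
- *That diagnosis is delayed by up to 45.6 months.* The figures are waits for one laboratory result. A clinical Pap or examination may find the lesion first.

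**Conclusion.** The point holds as a safety gap that is cheap to close. A site that follows the plan as written may lack a high-grade study result which section 8.0 says will lead to referral, chiefly where no concurrent clinical Pap was taken.

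The possible wait reaches 45.6 months, and is at least 20 months for a three-visit completer's first sample, only if results are held to 30 March 2019. The documents do not equate the end of the study with that date; section 6.5, for instance, describes close-out by site. The number affected and any diagnostic delay are unknown, and the Background gives no time scale for progression from which harm could be sized. Nothing here shows an effect on endpoints or conclusions. Confidence is medium, because the laboratory manual and consent templates may already provide for return of results.

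**What to change.** In 7.5.7.1, limit the sentence about late availability to HPV DNA typing, which can stay batched, and add:

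> Study cytology is read and reported on the screening laboratory's routine schedule after receipt of the vial, and the report is sent to the site investigator when issued. At minimum, HSIL or worse is sent within a set number of days of the laboratory receiving the vial (number to be agreed with the laboratory), and receipt is logged.

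The clock should start when the vial is received. No section supplied says when slides are read, so a limit counted from reading or issue could leave the same wait. If the laboratory manual or consent form already provides for this, a cross-reference in 7.5.7.1 is enough. Management stays with local algorithms.

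**Cost.** Low but not nil. The laboratory's report is already part of the plan, so no extra test or reader is needed, and this single cohort has no masked or randomised comparison to disturb. Reports must be relinked to participants and logged at up to 13 sites (5.0), which hold the identifying information (17.0). Some referrals will come earlier. If slides are currently read in late batches, reading would have to be brought forward.
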